10.10.2. Randomization Stratification

Randomization is stratified by dialysis type (HD or PD), region and by participation in an ABPM sub-study to ensure balance across treatment groups for both the overall parent study and within the ABPM sub-study. The prognostic stratification factors (i.e., dialysis type and region) will be taken into account within the analysis models. Stratification by ABPM sub-study participation was implemented for logistical reasons, and will not be taken into account within analysis models.

Baseline dialysis type strata will be identified by two data sources:

- PPD's IRT dataset
- eCRF

The proposed approach is to use the IRT strata in the adjusted analysis models in order to provide a randomization-based test statistic in accordance with the principle of 'analyze as randomized'. In summaries of subgroups however, the actual status of the factor for stratification derived from the eCRF form will be used. Additionally, subjects who change dialysis modality during the study will remain in the dialysis modality strata that was assigned at randomization.

200807

10.11. Appendix 11: Multiple Comparisons & Multiplicity

10.11.1. Handling of Multiple Comparisons & Multiplicity

10.11.1.1. Interim Analyses

The interim analysis will only result in stopping the study for harm or futility. There are no prospectively defined plans to stop any of the ASCEND trials early for benefit. As such, no multiplicity adjustments are required since the type I error rate will not be increased. Further details including stopping guidelines for harm and futility are included in the IDMC charter.

10.11.1.2. Final Analyses

The multiplicity strategy for this trial will use a combination of a gatekeeper approach on the co-primary endpoints, followed by a closed-test multiplicity procedure wrapped around the family of principal secondary analyses.

Figure 1 illustrates the structure of the statistical testing plan. First, the co-primary endpoints will be evaluated for at least non-inferiority by comparing each two-sided 95% CI to the appropriate non-inferiority margin. Then, the principal secondary analyses will be performed and superiority will be tested for the individual analyses. Conditional on both co-primary endpoints achieving non-inferiority (i.e., passing the gatekeeper), the family of principal secondary analyses will be formally tested for superiority using the widely known Holm-Bonferroni procedure [Holm, 1979]. The procedure will be conducted based on a family-wise Type I error rate set at the one-sided 2.5% level.

200807

[figure not shown]

Figure 1 Multiplicity controlled statistical testing plan

Details of the Holm-Bonferroni procedure for testing secondary endpoints:

The procedure starts with conducting the statistical analyses for each of the principal secondary analyses and ranking the resulting one-sided p-values from most significant (i.e. the lowest p-value) to the least significant. The Holm-Bonferroni formula is calculated for each rank using a target alpha. The formula for the Holm-Bonferroni method is:

$$Holm - Bonferroni_i = \frac{Target \, \alpha}{n - rank_i + 1}$$

[figure not shown]
Where:

- the *target* α is the overall alpha level (one-sided 2.5% significance)
- *n* is the total number of tests

The most significant p-value is compared to the rank-associated alpha derived from the Holm-Bonferroni method. If a positive statistically significant treatment effect is observed, then the testing continues to the next ranked test. If the endpoint fails to achieve statistical significance when compared to the Holm-Bonferroni rank-associated alpha, the testing stops and all subsequent endpoints are declared to have failed to achieve statistical significance. This algorithm is described in detail in Figure 2 for the four principal secondary analyses defined for the trial.

200807

Figure 2 The Holm-Bonferroni Procedure for Multiplicity Control

10.11.1.3. Subgroup Analyses

Subgroup analyses will not be adjusted for multiplicity.

200807

10.12. Appendix 12: Model Checking and Diagnostics for Statistical Analyses

10.12.1. Statistical Analysis Assumptions

Endpoint(s)	Hgb Change from Baseline to the EP		
Analysis	ANCOVA		
 obtaining values (i.e respective If there ar explored 	onal assumptions underlying the model used for analysis will be examined by a normal probability plot of the residuals and a plot of the residuals versus the fitted e. checking the normality assumption and constant variance assumption of the model ely) to gain confidence that the model assumptions are reasonable. The any departures from the distributional assumptions, alternative models will be using appropriate transformed data. ill be examined for treatment interactions with baseline Hgb and stratification factors		
Allalysis	Multiple Imputation/Tipping Point Analysis		
	 Intermittent missing data imputation: If there are error and or warning messages related to the by statement (e.g. not enough observations to fit regression models), try to impute by randomized treatment and baseline dialysis type, then by randomized treatment only until no error/warning messages. If convergence issue still occurs, the convergence precision may be 		
	set to 1E-3.		
	 Monotone missing data imputation: When imputing for each of the monotone missing dataset (out of the 200), if there are error and or warning messages related to the by statement and/or regression model (e.g. not enough observations with the Monotone statement), try 1) impute by randomized treatment and baseline dialysis type, with baseline Hgb and region as covariates, 2) impute by randomized treatment, with baseline Hgb, baseline dialysis type, and region as covariates, 3) impute by randomized treatment, with baseline Hgb, as covariates, 4) impute by randomized treatment with baseline Hgb as a covariate, until no error/warning messages. 		
Endpoint(s)	Time to first event endpoints: MACE and MACE or thromboembolic events or hospitalization for HF		
Analysis	Cox proportional hazards		
 hazards a estimated dialysis ty Should th methods 	on the validity of the adjusted Cox proportional hazards model, the proportional assumption will be assessed by plotting the logarithm of the negative logarithm of the l survivor function against the logarithm of time, for each treatment group, region and ype. If the hazards are proportional, the lines should be approximately parallel. ere be evidence of a violation of the proportional hazards assumption, the following may be considered:		
o Use c	 Use of a stratified Cox proportional hazards model (including prognostic factors in a 		

STRATA statement in PROC PHREG, rather than in the MODEL statement)							
Endpoint(s) Time to first event endpoints with death as a competing risk							
Analysis							
and one of then addit	 If there is a notable difference between one or both of all-cause mortality and non-CV mortality, and one or more of the secondary CV endpoints that do not include death as a component, then additional analysis methods to address competing risks may be pursued such as: Fine & Gray's Subdistribution Hazards (Fine, 1999) 						

200807

10.13. Appendix 13: Pharmacokinetic Sub-study Analysis Plan

10.13.1. Overview of Planned Pharmacokinetic Analyses

The pharmacokinetic (PK) analyses will be based on the "Pharmacokinetic" population, unless otherwise specified. The Pharmacokinetic population is defined as subjects for whom additional PK eligibility was confirmed and have at least one non-missing PK sample measurement.

Table 16 provides an overview of the planned analyses.

Table 16Overview of Planned Pharmacokinetic Analyses for GSK1278863,
and/or GSK2391220 (M2), GSK2506104 (M3) and GSK2531401 (M13)

Parameter	Untransformed						Log-Transformed							
		State	S	Summary		Individual		Stats Analysis		Summary		Individual		
	A	naly	sis		-				-	-		-		
	Т	F	L	Т	F	F	L	Т	F	L	Т	F	F	L
GSK1278863, GSK239122	20 (M2	2), G	SK25	06104	(M3)	and G	SK25	31401	(M13)		-		-
GSK1278863 and														
Metabolites Plasma														
Pharmacokinetic				Y	Y 1	Y	Y					Y 1	Y	
Concentration Time				Ŷ	Ϋ́	Ŷ	Ŷ					Ϋ́	Ŷ	
Data (ng/ml) by														
Treatment														
GSK1278863 and														
Metabolites Plasma				Y			Y				Y			
Pharmacokinetic				ř			ř				ř			
Parameter ² Data														
GSK1278863														
GSK1278863 Dose				Y			Y							
Parameter Data				ſ			ſ							
GSK1278863 Special				Y			Y				Y			
Parameter ³ Data											1			

NOTES:

- T = Table, F = Figure, L = Listings, Y = Display generated.
- Stats Analysis = Represents TFL related to any formal statistical analyses (i.e. modelling) conducted.
- Summary = Represents TFL related to any summaries (i.e. descriptive statistics) of the observed raw data.
- Individual = Represents FL related to any displays of individual subject observed raw data.
- 1. Mean and median plots will be generated

2. Cmax, Tmax, Ctau

3. Ctau/1mg Dose, Ctau/avg Dose EP TIR, Ctau/ avg Dose EP, Ctau/ Dose at MACE, Ctau/Final Dose for subjects without MACE, Ctau/ Dose at MACE++, Ctau/ Final Dose for subjects without MACE++, Cmax/1mg Dose, Cmax/avg Dose EP TIR, Cmax/avg Dose EP, Cmax/ Dose at MACE, Cmax/ Final Dose for subjects without MACE, Cmax/ Dose at MACE++, Cmax/ Final Dose for subjects without MACE, Cmax/ Dose at MACE++, Cmax/ Final Dose for subjects without MACE, Cmax/ Dose at MACE++, Cmax/ Final Dose for subjects without MACE, Cmax/ Dose at MACE++, Cmax/ Final Dose for subjects without MACE, Cmax/ Dose at MACE++, Cmax/ Final Dose for subjects without MACE, Cmax/ Dose at MACE++, Cmax/ Final Dose for subjects without MACE, Cmax/ Dose at MACE++, Cmax/ Final Dose for subjects without MACE++

10.13.2. Drug Concentration Measures

Refer to Appendix 5: Data Display Standards & Handling Conventions (Section 10.5.3 Reporting Process & Standards).

200807

10.13.3. Pharmacokinetic Parameters

10.13.3.1. Deriving Pharmacokinetic Parameters

- Refer to Appendix 5: Data Display Standards & Handling Conventions (Section 10.5.3 Reporting Process & Standards).
- The pharmacokinetic parameters of parent GSK1278863, and metabolites (GSK2391220 (M2), GSK2506104 (M3), and GSK2531401 (M13)) will be calculated by programming methods.
- All calculations of non-compartmental parameters will be based on actual sampling times.
- Pharmacokinetic parameters described in Table 17 will be determined from the plasma concentration-time data, as data permits.

Parameter	Parameter Description
GSK1278863,	GSK2391220 (M2), GSK2506104 (M3) and GSK2531401 (M13)
tmax	Time to reach Cmax, determined directly from the concentration-time data.
Ctau	Observed concentration at dosing interval (tau=24 h, predose sample)
Cmax	Maximum observed concentration, determined directly from the concentration-time data.
GSK1278863	
Avg Dose EP TIR	The average daily GSK1278863 dose when the subject is on-treatment and in target Hgb range during the evaluation period (EP) Weeks 28-52 (See Section 10.6.3.1). Evaluable Hgb values are used to determine time in range. Subjects who permanently stop randomized treatment before the beginning of the EP, and subjects who have 0% time in range (e.g., subjects who have an evaluable Hgb below or above range for the entire EP) will have a missing value for this parameter.
Avg Dose EP	The average daily GSK1278863 dose when the subject is on-treatment during the EP.
Dose at first MACE	The daily GSK1278863 dose at the time of the subject's first on-treatment adjudicated MACE. If the subject does not have an on-treatment adjudicated MACE, this value is missing.
Final Dose for Subjects without MACE	For subjects without an on-treatment adjudicated MACE, this is the subject's final GSK1278863 dose during the study.
Dose at first MACE++	The daily GSK1278863 dose at the time of the subject's first on-treatment adjudicated MACE++ (defined as the first adjudicated MACE, hospitalization for heart failure, or thromboembolic event) If the subject does not have an on-treatment adjudicated MACE++, this value is missing.
Final Dose for Subjects without MACE++	For subjects without an on-treatment adjudicated MACE++, this is the subject's final GSK1278863 dose during the study.
Ctau/1mg Dose	Ctau extrapolated to 1mg dose: Observed Ctau divided by dose administered on the PK day

Table 17Derived Pharmacokinetic Parameters for GSK1278863, and/or
GSK2391220 (M2), GSK2506104 (M3) and GSK2531401 (M13)

Parameter	Parameter Description
Ctau/Avg Dose EP TIR	Ctau extrapolated to average dose during EP TIR: Ctau/1mg multiplied by the average daily GSK1278863 dose when the subject is on-treatment and in target Hgb range during Weeks 28-52 (see Section 10.6.3.1). Evaluable Hgb values are used to determine time in range.
Ctau/Avg Dose EP	Ctau extrapolated to average dose during EP: Ctau/1mg multiplied by the average daily GSK1278863 dose during the EP.
Ctau/Dose at first MACE	Ctau extrapolated to dose at first on-treatment adjudicated MACE: Ctau/1mg multiplied by the daily GSK1278863 dose at the time of the subject's first on-treatment adjudicated MACE.
Ctau/Final Dose for subjects without MACE	For subjects without an on-treatment adjudicated MACE, this is the subject's Ctau/1mg multiplied by the subject's final daily GSK1278863 dose during the study.
Ctau/Dose at first MACE++	Ctau extrapolated to dose at first on-treatment adjudicated MACE++: Ctau/1mg multiplied by the daily GSK1278863 dose at the time of the subject's first on-treatment adjudicated MACE++.
Ctau/Final Dose for subjects without MACE++	For subjects without an on-treatment adjudicated MACE++, this is the subject's Ctau/1mg multiplied by the subject's final daily GSK1278863 dose during the study.
Cmax/1mg Dose	Cmax extrapolated to 1mg dose: Observed Cmax divided by dose administered on the PK day
Cmax/Avg Dose EP TIR	Cmax extrapolated to average dose during EP TIR: Cmax/1mg multiplied by the average daily GSK1278863 dose when the subject is on-treatment and in target Hgb range during Weeks 28-52 (see Section 10.6.3.1). Evaluable Hgb values are used to determine time in range.
Cmax/Avg Dose EP	Cmax extrapolated to average dose during EP: Cmax/1mg multiplied by the average daily GSK1278863 dose during the EP.
Cmax/Dose at first MACE	Cmax extrapolated to dose at MACE: Cmax/1mg multiplied by the daily GSK1278863 dose at the time of the subject's first on-treatment adjudicated MACE.
Cmax/Final Dose for subjects without MACE	For subjects without an on-treatment adjudicated MACE, this is the subject's Cmax/1mg multiplied by the subject's final daily GSK1278863 dose during the study.
Cmax/Dose at first MACE++	Cmax extrapolated to dose at MACE++: Cmax/1mg multiplied by the daily GSK1278863 dose at the time of the subject's first on-treatment adjudicated MACE++.
Cmax/Final Dose for subjects without MACE++	For subjects without an on-treatment adjudicated MACE++, this is the subject's Cmax/1mg multiplied by the subject's final daily GSK1278863 dose during the study.

200807

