2. SUMMARY OF KEY PROTOCOL INFORMATION

2.1. Changes to the Protocol Defined Statistical Analysis Plan

Changes to the originally planned statistical analysis specified in the fourth protocol amendment (Dated: 30JUL2020) are detailed as follows:

Table 1Changes to Protocol Defined Analysis Plan

Protocol	Reporting & Analysis Plan	
Statistical Analysis Plan	Statistical Analysis Plan	Rationale for Changes
None	 New displays related to COVID-19 pandemic have been added 	Assessing the impact of the COVID-19 pandemic
• None	 Number of RBC whole blood and transfusion event is included in the exploratory efficacy analysis of RBC and Whole Blood Transfusions 	 Number of RBC whole blood and transfusion event has been defined and included in the exploratory endpoints
• None	Time to first RBC and whole blood transfusion is included in the exploratory efficacy analysis of RBC and Whole Blood Transfusions	• Time to first RBC and whole blood transfusion has been included in the exploratory endpoints
None	Phosphate Binder analyses have been added	 Assessing the effect of Phosphate Binder co- administration.
None	 Clopidogrel analyses have been added 	 Assessing the effect of Clopidogrel co- administration.
PK Sub-study Statistical Analysis Plan	PK Sub-study Statistical Analysis Plan	Rationale for Changes
PK sub-study endpoints described as dose normalized	 PK sub-study endpoints described as dose extrapolated 	 Terminology clarification following discussion with regulatory agencies
 PK sub-study endpoints include: Scatter plots of daprodustat PK parameters (C_{tau} and C_{max}) dose normalized to 1 mg vs. percent time in range during EP. Scatter plots of average daprodustat dose during EP vs. percent time in range during EP. Scatter plots of daprodustat PK parameters (C_{tau} and C_{max}) dose normalized to average dose during EP vs. percent time in range during EP. 	 PK sub-study endpoints modified as follows: Endpoints removed: Scatter plots of daprodustat PK parameters (C_{tau} and C_{max}) dose normalized to 1 mg vs. percent time in range during EP. Scatter plots of average daprodustat dose during EP while in target Hgb range vs. percent time in range during EP. 	 Removed as these endpoints do not provide additional information for efficacy explorations than what will be available from remaining endpoints.

200807

Protocol	Reporting & Analysis Plan	
Statistical Analysis Plan	Statistical Analysis Plan	Rationale for Changes

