 Scatter plots of daprodustat PK parameters (C_{tau} and C_{max}) dose normalized to 1 mg vs. change from baseline of Hgb during EP. Boxplots of daprodustat PK parameters (Ctau and Cmax) dose normalized to 1 mg by subjects with or without MACE or combined safety endpoint 	 Scatter plots of daprodustat PK parameters (C_{tau} and C_{max}) dose normalized to average dose during EP while in target Hgb range vs. percent time in range during EP. Endpoints removed: Scatter plots of daprodustat PK parameters (C_{tau} and C_{max}) dose normalized to 1 mg vs. change from baseline of Hgb during EP. Endpoints removed: Boxplots of daprodustat PK parameters (Ctau and Cmax) dose normalized to 1 mg by subjects with or without MACE or combined safety endpoint 	
ABPM Sub-study Statistical Analysis Plan	ABPM Sub-study Statistical Analysis Plan	Rationale for Changes
Statistical analyses planned.	 No statistical analysis will be conducted for this sub- study due to the small number of subjects recruited. Instead all data will either be summarized or listed. 	 Small number of subjects recruited.

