- Number of days that a subject's evaluable Hgb is within the analysis range of 10-11.5 g/dL inclusive during the EP (See Section 10.6.1), including any unscheduled evaluable Hgb values that were taken during this time period.
- Use of unscheduled Hgb values follows the scenarios for unscheduled and multiple Hgb values.
- Linear interpolation is used to estimate Hgb between visits, accounting for any intermittent missing values (Rosendall, 1993).

Percent Time in Range During the EP

- Time in Range During the EP / [Earlier of (Date of the last evaluable Hgb value, Week 52 visit date) Later of (Date of the first evaluable Hgb value that between Week 16 and Week 52 inclusive, Week 28 visit date)]
- Note: Percent time in/below/above range during the EP is only defined for subjects with a
 Treatment Stop Date that is on or after their Week 28 visit date, and have at least two
 evaluable Hgb values on different days, where at least one evaluable Hgb value is contained
 within the EP and another evaluable Hgb value occurs within the range of the Week 16 visit
 through 4 weeks following the Week 52 visit, inclusive.

Time in Range During the MP

- Number of days that a subject's evaluable Hgb is within the analysis range of 10-11.5 g/dL inclusive between Weeks 28 and End of Study inclusive, including any unscheduled evaluable Hgb values that were taken during this time period.
- Linear interpolation is used to estimate Hgb between visits, accounting for any intermittent missing values (Rosendall, 1993).

Percent Time in Range During the MP

• Time in Range During the MP / [Earlier of (Date of the last evaluable Hgb value, End of study date)– Later of (Date of the first evaluable Hgb value that is on or after week 16, Week 28 visit

200807

Time In Range

date)]

Note: Percent time in/below/above range during the MP is only defined for subjects with a
Treatment Stop Date that is on or after their Week 28 visit date, and have at least two
evaluable Hgb values on different days, where at least one evaluable Hgb value is contained
within the MP and another evaluable Hgb value occurs within the range of the Week 16 visit
through the Treatment Stop Date + 1 day.

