10.13.4. Pharmacokinetic / Pharmacodynamic Analyses

- The primary goal of this analysis is to characterize the pharmacokinetic/pharmacodynamic relationship of parent GSK1278863 and efficacy and safety endpoints in the "Pharmacokinetic" population from this study.
 - The influence of subject demographics and baseline characteristics, including disease activity in this population may be investigated.
- A summary of the planned population pharmacokinetic/pharmacodynamic analyses are outlined below:
 - Relationships between drug exposure and selected efficacy, MACE and MACE
 ++ events will be explored and characterized as data permit. The exposure will be estimated on the sparse PK collected in a sub-set of the study population. The data may be dose- extrapolated to the dose administered during the PK collection period. Any changes to the proposed analyses would be described in the CSR.

Table 18Overview of Planned Pharmacokinetic / Pharmacodynamic Analyses
for GSK1278863

Parameter			Un	trans	formed	k		Log-Transformed						
		Stats		Sum	mary	Indiv	vidual	Stat	s Ana	lysis	Sum	mary	Indiv	vidual
	_A	nalys	is	L	-									
	T	F	L	T	F	F		T	F	L	Т	F	F	L
GSK1278863	1	1	T	1			1		1	1				
Scatter plot of % Time														
Evaluable Hgb in Range						Y								
during EP vs. Avg Dose EP TIR														
Scatter plot of Evaluable														
Hgb Change from						Y								
Baseline during EP vs.						•								
Avg Dose EP														
Scatter plot of % Time														
Evaluable Hgb in Range						Y								
during EP vs. Ctau/Avg Dose EP TIR														
Scatter plot of														
Evaluable Hgb Change														
from Baseline during						Y								
EP vs. Ctau/Avg Dose														
EP														
Boxplot of Ctau/Dose at														
on-treatment MACE or														
MACE++ by subjects with						Y								
or without on-treatment														
MACE or MACE++														
Scatter plot of % Time														
Evaluable Hgb in Range						Y								
during EP vs. Cmax/Avg														

200807

Parameter		Untransformed								Log-Transformed						
		Stat	S	Sum	mary	Indiv	vidual	Stat	s Ana	lysis	Sum	mary	Indiv	vidual		
	A	naly	sis													
	Т	F	L	Т	F	F	L	Т	F	L	Т	F	F	L		
Dose EP TIR																
Scatter plot of																
Evaluable Hgb Change						v										
from Baseline during EP						I										
vs. Cmax/Avg Dose EP																
Boxplot of Cmax/Dose at																
on-treatment MACE or																

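### The three PK plots of % time in range use a dose averaged only over in-range days, so subjects with 0% time in range cannot appear in them

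*SAP*

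**What the plan says.** SAP Section 10.13.3.1, Table 17, defines Avg Dose EP TIR as "The average daily GSK1278863 dose when the subject is on-treatment and in target Hgb range during the evaluation period (EP) Weeks 28-52". The parameter is missing for subjects who stop randomized treatment for good before the evaluation period (EP), and for "subjects who have 0% time in range (e.g., subjects who have an evaluable Hgb below or above range for the entire EP".

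Two exposure parameters inherit that dose: "Ctau extrapolated to average dose during EP TIR" and "Cmax extrapolated to average dose during EP TIR". Each multiplies the concentration per 1 mg by Avg Dose EP TIR.

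Section 10.13.4, Table 18, lists three scatter plots of % time evaluable Hgb in range. The first has its x-axis "during EP vs. Avg Dose EP TIR"; the other two use the Ctau and Cmax versions. All three are marked only as individual figures.

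Table 17 also defines Avg Dose EP, Ctau/Avg Dose EP and Cmax/Avg Dose EP, with no exclusion at 0%. Table 18 pairs these only with Hgb change from baseline.

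Section 10.6.3.1 defines the numerator of the outcome as "Number of days that a subject's evaluable Hgb is within the analysis range of 10-11.5 g/dL" inclusive during the EP.

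**The concern.** A scatter plot meant to show how an outcome varies with exposure should not drop subjects because of that outcome. Here the x value exists only if the y value is above zero. Subjects below range throughout and subjects above range throughout have a known outcome and a known average dose, yet they cannot be drawn.

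For the remaining subjects the x value is still conditioned on y: someone in range for a few days is represented by the dose of those days alone.

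Section 10.13.4 gives the primary goal as characterizing the relationship between drug exposure and the efficacy and safety endpoints. A reader of these three figures would see no one with complete failure on the outcome, and could take time in range to be better, or less related to exposure, than it is.

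**Working it through.** The SAP states no expected share at 0% and no planned statistic for these plots, so there is no figure to reproduce. The main check is one of definitions.

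**1. Is 0% a valid outcome?** Under Section 10.6.3.1, % time in range needs a treatment stop date on or after the Week 28 visit and two evaluable Hgb values on different days: one in the EP, and another between Week 16 and 4 weeks after Week 52. It is in-range days divided by observed days. The EP spans 52 - 28 = 24 weeks, or 24 x 7 = 168 days. A subject out of range on one side throughout has 0/168 = 0%, which is defined.

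**2. Is x defined for that subject?** Avg Dose EP TIR is the dose summed over in-range days divided by the number of in-range days. With zero such days it has no value, and Table 17 sets it to missing. The Ctau and Cmax versions are multiples of it, so they are missing too. No point can therefore lie at y = 0 in any of the three plots.

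**3. Does the other exclusion matter?** Stopping treatment before the EP leaves % time in range undefined as well, so it removes no valid outcome. Only the 0% rule does.

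**4. What does x mean for a subject briefly in range?** With 10 in-range days, y = 10/168 = 6.0% and x is the dose on those 10 days, not over the other 158.

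**5. Which range?** Table 17 says target range, which the synopsis in Section 1 gives as 10-11 g/dL, but cites Section 10.6.3.1, which uses 10-11.5 g/dL. Read literally, a subject between 11 and 11.5 g/dL throughout would have y = 100% and no in-target days from which to form x.

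**6. Illustration of size.** Every input here is an assumption, none from the SAP: 20,000 subjects; 7 four-weekly values with linear interpolation; range 10-11.5 g/dL; mean Hgb 10.5 g/dL at average resistance; average dose 4 x exp(0.7r) for resistance r (standard normal); subject mean Hgb lowered by slope x r; current dose higher when Hgb is below the subject's own mean. Rho is the Spearman correlation of dose with % time in range.

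| Between SD, within SD, slope (g/dL) | Share at 0% | Rho, Avg Dose EP, all subjects | Rho, Avg Dose EP TIR, 0% dropped | Mean time in range, top dose fifth: all / 0% dropped |
|---|---|---|---|---|
| 0.5, 0.6, 0.2 | 2.5% | -0.164 | -0.092 | 58.0% / 61.5% |
| 0.5, 0.6, 0.5 | 5.9% | -0.251 | -0.154 | 37.5% / 45.8% |
| 0.8, 0.5, 0.5 | 16.0% | -0.145 | -0.044 | 38.4% / 54.9% |
| 0.8, 0.5, 0.9 | 26.4% | -0.170 | -0.054 | 19.8% / 43.6% |

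A similar simulation with exposure-Hgb correlation -0.5, within-subject SD 0.6 and between-subject SD 0.4 to 0.6 drops only 0.7% to 3.5%. The exclusion alone then moves rho from -0.21 to -0.20, or from -0.18 to -0.15. With mean Hgb at 10.75 g/dL, the centre of the range, rho is about 0 either way.

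**The case against.** The strongest reply is that nothing inferential is at stake. Table 18 plans no model, correlation, group mean or test for these plots; the statistics in the illustration are not ones the SAP will report. The ITT time-in-range analysis in Section 8.1.2.2 is separate and treats 0% as an ordinary value. This stands, and it limits the point to what the figures show.

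The omitted subjects are also not lost from the PK/PD displays. Hgb change is plotted against the three Avg Dose EP parameters, where low and high responders separate instead of both falling at zero. A reader might infer that these subjects disappear from the sub-study; they do not. They are missing from three of the six efficacy scatter plots.

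The in-range dose answers a coherent question, namely at what dose a subject is in range, and its missing-value rule is openly stated. That supports keeping it, but not as the only x-axis for time in range.

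Dose is titrated to Hgb in this trial, so Avg Dose EP is itself partly a consequence of response. That is right: the replacement restores the missing points but does not make the plots causal.

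A reader might also infer an unexplained departure from the protocol. The change table in SAP Section 2.1 carries both "dose normalized to average dose during EP vs. percent time in range during EP" and "dose normalized to average dose during EP while in target Hgb range vs. percent time in range during EP". Its layout does not survive extraction well enough to show which entries were removed and which were changed, and it describes superseded text. Nothing here rests on it.

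On the range, the cross-reference to Section 10.6.3.1 largely settles the meaning, so this is a wording correction.

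**Conclusion.** The point holds as a matter of definition. All three % time-in-range plots use an exposure that depends on the outcome and is missing by rule at 0%, so subjects with a valid outcome are dropped because of that outcome. This follows from Tables 17 and 18 and Section 10.6.3.1 and needs no assumption.

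Its size is unknown. In the illustrations the share dropped ran from 0.7% to 26%, with an effect on the visible relation from almost none to marked. A reader might want to quote a set percentage of attenuation, but any such figure would reflect the assumed standard deviations and not this trial. The direction, a weaker apparent relation and higher time in range at high dose, also assumes that resistant subjects receive more drug and have lower Hgb.

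The importance is low. These are descriptive sub-study figures; the co-primary, principal secondary and ITT time-in-range analyses are untouched.

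**What to change.** - In Table 18, plot % time in range against Avg Dose EP, Ctau/Avg Dose EP and Cmax/Avg Dose EP, with subjects at 0% shown at y = 0.
- Keep the three in-range-dose plots, if wanted, as secondary displays. State on each the number of subjects excluded at 0%, split into below and above range.
- In Table 17, replace the target-range wording with the 10-11.5 g/dL analysis range of Section 10.6.3.1.
- Note on the figures that dose is titrated to Hgb, so the plots are descriptive and not causal.

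The cost is three replaced or added figures and a few lines of SAP text. No new data and no new parameter are needed.
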